5 ADDITIONAL CONSIDERATIONS

5.1 Duration of Response

Duration of overall response: The duration of overall response is measured from the time measurement criteria are first met for CR/PR (whichever is first recorded) until the first date that recurrent or PD is objectively documented (taking as reference for PD the smallest measurements recorded on study).

The duration of overall CR is measured from the time measurement criteria are first met for CR until the first date that recurrent disease is objectively documented.

Duration of SD: SD is measured from the start of the treatment (in randomized trials, from date of randomization) until the criteria for progression are met, taking as reference the smallest sum on study (if the baseline sum is the smallest, this is the reference for calculation of PD).

5.2 Lesions that Disappear and Reappear

If a lesion disappears and reappears at a subsequent timepoint, measurement should be continued. However, the patient's response at the point in time when the lesion reappears will depend upon the status of his/her other lesions. For example, if the patient's tumor had reached a CR status and the lesion reappeared, then the patient would be considered PD at the time of reappearance. In contrast, if the tumor status was a PR or SD and 1 lesion that had disappeared then reappears, its maximal diameter should be added to the sum of the remaining lesions for a calculated response; in other words, the reappearance of an apparently 'disappeared' single lesion among many that remain is not in itself enough to qualify for PD; this requires the sum of all lesions to meet the PD criteria. The rationale for such a categorization is based upon the realization that most lesions do not actually 'disappear' but are not visualized because they are beyond the resolving power of the imaging modality employed.

Reference:

¹ Eisenhauer EA, Therasse P, Bogaerts J, et al. New response evaluation criteria in solid tumours: Revised RECIST guideline (version 1.1). Eur J Cancer 2009;45:228-47.

APPENDIX 7 WOMEN OF CHILDBEARING POTENTIAL DEFINITIONS AND METHODS OF CONTRACEPTION

At a minimum, subjects must agree to use one highly effective method of contraception as listed below:

HIGHLY EFFECTIVE METHODS OF CONTRACEPTION

Highly effective methods of contraception have a failure rate of < 1% when used consistently and correctly. Women of childbearing potential (WOCBP) and female partners of male subjects, who are WOCBP, are expected to use 1 of the highly effective methods of contraception listed below. Male subjects must inform their female partners who are WOCBP of the contraceptive requirements of the protocol and are expected to adhere to using contraception with their partner. Contraception methods are as follows:

- 1. Progestogen only hormonal contraception associated with inhibition of ovulation.
 - Hormonal methods of contraception including oral contraceptive pills containing combined estrogen + progesterone, vaginal ring, injectables, implants and intrauterine devices (IUDs) such as Mirena®
- 2. Non-hormonal IUDs, such as ParaGard®
- 3. Bilateral tubal occlusion
- 4. Vasectomized partner with documented azoospermia 90 days after procedure
 - Vasectomized partner is a highly effective birth control method provided that partner is the sole sexual partner of the WOCBP trial participant and that the vasectomized partner has received medical assessment of the surgical success.
- 5. Intrauterine hormone-releasing system.
- 6. Complete abstinence
 - Complete abstinence is defined as the complete avoidance of heterosexual intercourse (refer to Glossary of Terms)
 - Complete abstinence is an acceptable form of contraception for all study drugs and must be used throughout the duration of the study treatment (plus 5 half-lives of the investigational drug plus 30 days).
 - It is not necessary to use any other method of contraception when complete abstinence is elected.
 - Subjects who choose complete abstinence must continue to have pregnancy tests.
 - Acceptable alternate methods of highly effective contraception must be discussed in the event that the subject chooses to forego complete abstinence.
 - The reliability of sexual abstinence needs to be evaluated in relation to the duration of the clinical trial and the preferred and usual lifestyle of the subject.

UNACCEPTABLE METHODS OF CONTRACEPTION

- 1. Periodic abstinence (calendar, symptothermal, post-ovulation methods)
- 2. Withdrawal (coitus interruptus)

- 3. Spermicide only
- 4. Lactation amenorrhea method

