iii) Adequate renal function with a serum creatinine of $< 1.5 \times ULN$ or a creatinine clearance (CrCl) > 40 mL/min using Cockcroft-Gault formula below:

Female CrCl = $(140 - age in years) \times weight in kg \times 0.85$ $72 \times serum creatinine in mg/dL$ Male CrCl = $(140 - age in years) \times weight in kg \times 1.00$ $72 \times serum creatinine in mg/dL$

- k) Ability to comply with treatment, PK and research sample collection (when indicated), and required study follow-up.
- Subject Re-enrollment: This study permits the re-enrollment of a subject that has discontinued the study as a pretreatment failure (ie, subject has not been treated). If re-enrolled, the subject must be re-consented.

3) Age and Reproductive Status

- a) Males and Females, ages 18 or age of majority
- b) Women of childbearing potential (WOCBP) must have a negative serum or urine pregnancy test (minimum sensitivity 25 IU/L or equivalent units of human chorionic gonadotropin) within 24 hours prior to the start of study drug.
- c) Women must not be breastfeeding.
- d) WOCBP must agree to follow instructions for method(s) of contraception for the duration of treatment with study drug (s) BMS-986183 monotherapy plus 5 half-lives of study drug plus 30 days (duration of ovulatory cycle) for a total of 90 days post-treatment completion (BMS-986183 dose escalation [Part 1] and BMS-986183 dose expansion [Part 2]). WOCBP must agree to follow instructions for method(s) of contraception for the duration of study treatment with nivolumab and 5 months (150 days) after the last dose of study drug (ie, 30 days [duration of ovulatory cycle] plus the time required for the study drug to undergo approximately 5 half-lives) (BMS-986183 and nivolumab dose escalation [Part 3] and BMS-986183 and nivolumab dose expansion [Part 4]).

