- e) Males who are sexually active with WOCBP must agree to follow instructions for method(s) of contraception for the duration of treatment with study drug (s) BMS-986183 plus 5 half-lives of the study drug plus 90 days (duration of sperm turnover) for a total of 150 days post-treatment completion (BMS-986183 dose escalation [Part 1] and BMS-986183 dose expansion [Part 2]). Males who are sexually active with WOCBP must agree to follow instructions for method(s) of contraception for the duration of study treatment with nivolumab and 7 months (210 days) after the last dose of study drug (ie, 90 days [duration of sperm turnover] plus the time required for the study drug to undergo approximately 5 half-lives). In all study parts, male subjects must be willing to refrain from sperm donation during the time described above.
- f) Azoospermic males are exempt from contraceptive requirements. WOCBP who are continuously not heterosexually active are also exempt from contraceptive requirements and still undergo pregnancy testing as described in this section.

Investigators shall counsel WOCBP and male subjects who are sexually active with WOCBP on the importance of pregnancy prevention and the implications of an unexpected pregnancy. Investigators shall advise on the use of highly effective methods of contraception, which have a failure rate of < 1% when used consistently and correctly. Refer to Appendix 7.

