10 GLOSSARY OF TERMS

Term	Definition
Complete Abstinence	Complete Abstinence is defined as complete avoidance of heterosexual intercourse and is an acceptable form of contraception for all study drugs. This also means that abstinence is the preferred and usual lifestyle of the patient. This does not mean periodic abstinence (eg, calendar, ovulation, symptothermal, profession of abstinence for entry into a clinical study, post-ovulation methods) and withdrawal, which are not acceptable methods of contraception. Women must continue to have pregnancy tests. Acceptable alternate methods of highly or less effective contraceptives must be discussed in the event that the subject chooses to forego complete abstinence.
Additional Research	Those scientific activities which cannot be reasonably anticipated at the time of study design, for which we would like to collect and/or retain samples from study participants. Examples of additional research include, but are not limited to, new assay development and validation, companion diagnostic development, new hypotheses in the interaction of drug and the human body, and exploration of emerging science in the understanding of disease.

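### Appendix 7 gives one abstinence period not labelled by sex, 60 days shorter than the 3.3.1 window for men, and the glossary differs from Appendix 7 on alternatives to abstinence

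*Protocol*

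**What the plan says.** **Duration.** Section 3.3.1 sets separate windows by sex and by treatment.

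- Item 3(d), WOCBP on monotherapy (Parts 1 and 2): "plus 5 half-lives of study drug plus 30 days (duration of ovulatory cycle) for a total of 90 days post-treatment completion".
- Item 3(d), WOCBP in Parts 3 and 4: "5 months (150 days) after the last dose of study drug (ie, 30 days [duration of ovulatory cycle] plus the time required" for about 5 half-lives.
- Item 3(e), men sexually active with WOCBP, monotherapy: "plus 5 half-lives of the study drug plus 90 days (duration of sperm turnover) for a total of 150 days post-treatment completion".
- Item 3(e), the same men with nivolumab: "7 months (210 days) after the last dose of study drug (ie, 90 days [duration of sperm turnover] plus the time required" for about 5 half-lives.

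Appendix 7 item 6 gives one period for abstinence: "must be used throughout the duration of the study treatment (plus 5 half-lives of the investigational drug plus 30 days". It has no qualifier by sex or by Part. The introduction to the same list covers both groups: "Women of childbearing potential (WOCBP) and female partners of male subjects, who are WOCBP, are expected to use 1 of the highly effective methods". It adds that male subjects should tell their partners of the requirements and use contraception with them. Section 3.3.1 closes its reproductive criteria by sending investigators to Appendix 7 when they counsel WOCBP and men sexually active with WOCBP.

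**Method standard.** Appendix 7 opens with a floor: "At a minimum, subjects must agree to use one highly effective method of contraception as listed below". For a subject who gives up abstinence, it mentions only highly effective alternatives. The glossary entry on complete abstinence, which Appendix 7 cites for the definition, says: "Acceptable alternate methods of highly or less effective contraceptives must be discussed in the event that the subject chooses to forego complete abstinence".

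**The concern.** A site that uses Appendix 7 as its working reference on contraception finds one end date for abstinence. The accepted methods there serve men as well as women, and no other period for men appears. A man whose method is abstinence can therefore be given two different end dates, depending on which page is read. On the second point, a site that follows the appendix's pointer to the glossary meets a weaker description of what may replace abstinence.

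What is at stake is subject and partner protection. This is a first-in-human study of a conjugate carrying a microtubule inhibitor. The protocol itself ties the longer window for men to sperm turnover, and section 6.4 asks for partner pregnancies to be reported. No statistical quantity depends on the answer.

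**Working it through.** **Inputs.** The four day totals and their added days (30 for WOCBP, 90 for men) come from 3.3.1 items 3(d) and 3(e). The rule of 5 half-lives plus 30 days comes from Appendix 7 item 6. The readable text gives no half-life for BMS-986183, so the check is one of internal consistency.

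**Step 1: reproduce the plan's totals for men.**

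- Monotherapy: the WOCBP total implies 5 half-lives = 90 − 30 = 60 days. Then 60 + 90 = 150 days, as item 3(e) states.
- With nivolumab: the WOCBP total implies 150 − 30 = 120 days. Then 120 + 90 = 210 days, as item 3(e) states.

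So the totals in 3.3.1 agree with one another.

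**Step 2: put the same half-lives into Appendix 7 item 6.**

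| Setting | Item 6 | 3(d), WOCBP | 3(e), men | Item 6 against 3(e) |
|---|---|---|---|---|
| Monotherapy | 60 + 30 = 90 | 90 | 150 | 60 days shorter |
| With nivolumab | 120 + 30 = 150 | 150 | 210 | 60 days shorter |

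Item 6 reproduces the WOCBP window exactly and falls short of the window for men by the same amount in both settings.

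**Step 3: does the gap depend on the half-life?** Write H for 5 half-lives. Then (H + 90) − (H + 30) = 60 days for any H. For example, section 1.4.1.2 gives a nivolumab half-life of 26.7 days, so H = 5 × 26.7 = 133.5. The two windows become 163.5 and 223.5 days, again 60 days apart. Setting 163.5 against the stated 210 would mix two half-lives (133.5 and 120 days for H) and is not a valid comparison.

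**Step 4: method standard.** No arithmetic applies. Appendix 7 requires at least one highly effective method and names only such methods as alternatives to abstinence. Section 3.3.1 tells investigators to advise on highly effective methods. The glossary sentence is nearly the same as the Appendix 7 sentence but widens the class to include less effective methods. The two sentences cannot both describe the intended standard.

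**The case against.** The strongest reply is that item 6 is simply the women's rule without a label. The appendix is titled for WOCBP. A nearby bullet requires continued pregnancy tests, which fits only women. The added 30 days is the ovulatory-cycle allowance of item 3(d). On that reading item 6 and 3(d) agree, and the period for men is set in 3(e), an inclusion criterion that section 3.3 says admits no exceptions. It can also be said that 3.3.1 points to Appendix 7 for methods rather than for durations.

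Much of this stands, and it rules out three stronger readings that a reader might infer.

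- That Appendix 7 sets the shorter period for every subject. It does not say so. The sentence is unqualified, which is a weaker statement.
- That a man is released from contraception when the item 6 period ends. If he then becomes sexually active with a WOCBP, he is within the terms of 3(e) and its longer window is still running. Nothing in Appendix 7 overrides it.
- That the glossary authorises weaker methods. It says that alternatives must be discussed, and the floor in Appendix 7 remains.

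The reply does not remove the conflict. Appendix 7 speaks to male subjects directly, offers them the same list that contains abstinence, and gives them no other period. Section 3.3.1 sends investigators there for men by name. A reader has to work out from context that the bracketed duration is not meant for men.

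**Conclusion.** The point holds as an internal inconsistency between operative passages. It is not a design choice and not an override of 3.3.1. As written, the abstinence period in Appendix 7 is 60 days shorter than the 3(e) window for men, on monotherapy and with nivolumab alike. The effect is confined to men who rely on abstinence and are or may become sexually active with WOCBP; azoospermic men are exempt under 3.3.1.

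The day figures rest on the half-life allowances implied by the 3.3.1 totals (60 and 120 days). For Parts 3 and 4 they also assume that item 6, which names a single investigational drug without saying which, means nivolumab. That is the reading under which it matches 3(d).

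The difference over alternatives to abstinence is a second, separate wording conflict with no number attached. Both deserve correction because they concern contraception in a first-in-human study. Neither bears on an endpoint, sample size, decision rule or analysis.

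**What to change.** The sponsor should reconcile 3.3.1 items 3(d) and 3(e), the glossary entry on complete abstinence, and Appendix 7 item 6. Two edits would do it.

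- State the duration in one place. For example, item 6 could cross-refer to the windows by sex and Part in 3.3.1 instead of carrying its own period.
- Make the glossary and Appendix 7 sentences on alternatives to abstinence say the same thing.

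Which period and which method standard stand is for the sponsor to decide; this review takes no view. The cost is two wording changes in a protocol amendment. No data collection, procedure or analysis changes.

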APPENDIX 8 NYHA CLASSIFICATION

NYHA Classification

Class I	Subjects with no limitation of physical activity; ordinary physical activity does not cause undue fatigue, palpitation, or dyspnea (shortness of breath).
Class II	Subjects with slight limitation of physical activity; they are comfortable at rest, but ordinary physical activity results in fatigue, palpitation, or dyspnea.
Class III	Subjects with marked limitation of physical activity; they are comfortable at rest, but less than ordinary activity causes fatigue, palpitation, or dyspnea.
Class IV	Subjects who are unable to carry out any physical activity without discomfort; they have symptoms of cardiac insufficiency at rest; if any physical activity is undertaken, discomfort is increased.

NYHA = New York Heart Association.

2 STUDY DESCRIPTION

2.1 Study Design

This is a Phase 1/2, open-label study to characterize the safety and tolerability of BMS-986183 administered as a single agent and in combination with nivolumab to subjects with HCC. The study has 4 parts: Part 1 (Phase 1 - BMS-986183 dose escalation), Part 2 (Phase 2 - BMS 986183 dose expansion), Part 3 (Phase 1 - BMS-986183 and nivolumab dose escalation), and Part 4 (Phase 2 - BMS 986183 and nivolumab dose expansion). BMS 986183 dose escalation (Part 1) and BMS 986183 and nivolumab dose escalation (Part 3) will include subjects with HCC who have received and either progressed or been refractory or intolerant to at least 1 standard prior systemic treatment regimen. BMS 986183 dose expansion (Part 2) will include only subjects with HCC who have progressed or been refractory to at least 1 standard prior systemic treatment regimen (and not received more than 2 prior systemic treatments) AND with a plasma membrane or cytoplasmic H score ≥ 50 for GPC 3 expression in the tumor tissue. The dose chosen for BMS 986183 dose expansion (Part 2) will be based on results (safety, PK, and all available data) from BMS-986183 dose escalation (Part 1). BMS 986183 and nivolumab dose expansion (Part 4) will include subjects who have received no prior systemic therapy for HCC AND with a plasma membrane or cytoplasmic H score ≥ 50 for GPC-3 expression in the tumor tissue. The dose chosen for BMS 986183 and nivolumab dose expansion (Part 4) will be based on results (safety, PK, and all available data) from BMS-986183 and nivolumab dose escalation (Part 3). See [Figure 2.1- 1](#) below for a schematic of the study design

[figure not shown]
Figure 2.1- 1: Study Design

1L = first-line; 2L = second-line; IV = intravenous; Q3W = every 3 weeks; Ref = refractory; Rel = relapse.

All subjects will complete up to 4 study periods: screening (up to 28 days), treatment (for approximately 1 year or 17 cycles, with 21 days/cycle), safety follow-up (for a total of 60 days after the last dose of study drug for BMS-986183 dose escalation (Part 1) and BMS 986183 dose expansion (Part 2) and for a total of 100 days after the last dose of study drug for BMS 986183 and nivolumab dose escalation (Part 3) and BMS 986183 and nivolumab dose expansion (Part 4)), with simultaneous response and survival follow-up periods. All subjects will continue to be followed up to 6 months from last dose of study drug. Subjects in BMS 986183 and nivolumab dose escalation (Part 3) and BMS 986183 and nivolumab dose expansion (Part 4) may also be eligible for retreatment with their originally assigned dose regimen with disease progression during follow-up. Only subjects in BMS-986183 dose expansion (Part 2) who have disease progression may be eligible for a combination therapy extension option (their current BMS-986183 dose + flat dose of nivolumab, provided that this combination dose has been found to be safe from BMS-986183 and nivolumab dose escalation (Part 3)). Subjects treated with BMS-986183 and nivolumab combination therapy may be permitted to continue combination therapy beyond initial RECIST v1.1-defined PD, as assessed by the investigator, as long as they meet the criteria specified in the protocol (Section 4.5.7). See [Figure 2.1- 2](#) for a schematic of study periods

Figure 2.1- 2: Dosing (Every 3 Weeks) and Study Periods

^a DLT Assessment Period is only for BMS-986183 dose escalation (Part 1) and BMS-986183 and nivolumab dose escalation (Part 3).

^b Response follow-up is simultaneous with survival follow-up. Only subjects with SD, PR, or CR will be followed for response at least every 3 to 4 months until progression, death, or initiation of new treatment (whichever occurs first).

C = Cycle 1 D = Day.

A total of approximately 151 subjects will be treated in the entire study, with approximately up to 30 subjects in BMS-986183 dose escalation (Part 1), approximately 50 subjects in BMS-986183 dose expansion (Part 2), approximately 21 subjects in BMS-986183 and nivolumab dose escalation (Part 3), and approximately 50 subjects in BMS-986183 and nivolumab dose expansion (Part 4). The approximate duration of the study is 4 years from the time of the first visit of the first subject to when the last subject has been followed for at least 6 months from his/her last date of treatment.

2.2 Treatment Assignment

After informed consent has been obtained, the subject must be enrolled into the study by using an interactive response technology (IRT) to obtain the subject number.

In BMS 986183 monotherapy dose escalation (Part 1) and BMS 986183 and nivolumab combination therapy dose escalation (Part 3), if a subject discontinues treatment with BMS-986183 during the DLT period for reasons other than DLT, the subject may be replaced if necessary for safety assessments. Replacement subjects will receive the same treatment but will be assigned a new subject number.

Subjects may be permitted to rescreen for the study following agreement between the Sponsor/Medical Monitor and investigators.

2.3 Blinding and Unblinding

Not Applicable.

2.4 Protocol Amendments

Table 2.4- 1: List of Protocol Amendments

Amendment number	Date	Summaries
1	29-Jun-2016	Changes include clarification of dose escalation decisions, clarification of hepatic DLT definition, insertion of additional ECHO/MUGA scans, clarification of additional research language, insertion of exclusion criteria for cytochrome P450 3A4 inhibitors, correction of typographical errors
2	21-Mar-2017	Added dose escalation and expansion arms combining BMS-986183 and nivolumab, including revision of the study objectives, select eligibility criteria, [REDACTED], follow-up visit schedule, and statistical analyses; updates to the overall risk/benefit assessment; and revision of dose-limiting toxicity, dose modification, dose delay, study drug re-initiation, and study therapy discontinuation criteria to align monotherapy and combination therapy. [REDACTED] [REDACTED] Updated BMS-986183 monotherapy product development and risk/benefit assessments with recent study data. Clarified age criteria to include subjects 18 or age of majority. Added the option for treatment beyond disease progression for subjects treated with BMS-986183 and nivolumab combination therapy. Added option to receive combination therapy following disease progression in BMS-986183 monotherapy dose expansion (Part 2). Updated the prior monotherapy analyses relevant to hepatocellular cancer and immune response, [REDACTED] and mandatory and optional tumor biopsy requirements. [REDACTED] Revised study design so that subjects with complete response that is confirmed at the next cycle will discontinue treatment and added that additional subjects may be added to BMS-986183 monotherapy dose escalation (Part 1) to satisfy regional/local requirements (e.g., in Chinese subjects where weight or genetic factors may play a role in safety, pharmacokinetics, and pharmacodynamics). Moved contraception information to an appendix, per BMS standards. Infusion reaction management text was removed to reduce redundancy with Section 3.7, Infusion Reactions. Clarified that there will be no individual dose escalations of BMS-986183, added information and a cross-reference regarding infusion reactions, and added cross-reference for dosing modifications. Added that intra-subject dose escalation is not allowed. Updated information for vital signs assessments and targeted physical examination. Clarified image collection and review and clarified that de-identified scans will be used. [REDACTED] Changed additional research text so that prospective samples will not be collected. Changed the language describing when subjects will resume study therapy. Removed requirement for formalin-fixed, paraffin embedded tumor samples. Updated Study Director/Central Medical Monitor address. Minor modifications, corrections, and other clarifications have been made throughout the protocol, including updates required to align with current BMS standards.

[figure not shown]
